Subjects who meet eligibility criteria based on the results of the questionnaires and phone bioscreen will be invited to the in-person interview with the PI at the UC San Diego Health Eating Disorders Center for Treatment and Research. At the start of the study visit, the PI or research coordinator will review the consent form with the subject, will answer any questions about the study and will assess comprehension of the study procedures, benefits, and risks. Subjects will then sign a new consent form and a signed and dated copy of the completed consent form will be given to the subject.

[name] will meet with each subject to complete the diagnostic assessment (SCID-5) and comprehensive medical interview with the subject to determine study eligibility.

After eligibility is confirmed, the subject will complete a swallow test where she will be given an empty pill capsule and will be asked to swallow to make sure she will not have any issues with the size of the medication capsules. If the subject cannot swallow this size capsule or feels she will not be able to, she may be withdrawn from the study at that point.

The subject will be scheduled for the Pre-Scan Visit and 3 MRI scans. The MRI scans will be scheduled 2 to 4 days apart (3 days apart is ideal).

Pre-Scan Visit

Location: Altman Clinical Trials Research Center ([name])

Subjects will complete a pre-scan visit at ACTRI to complete a blood draw and electrocardiogram (EKG). This visit will occur no more than 1 week before Study Visit 1 is scheduled. At this visit ACTRI research nursing staff (certified phlebotomist) will complete the blood draw (about 2 tablespoons blood). An EKG will be performed, and results of the EKG and blood tests will be sent to the PI for review. The following tests will be processed through the Center for Advanced Laboratory Medicine (CALM): Creatinine; BUN; electrolytes; serum pregnancy test. If the PI feels the results are out of range he may withdraw the subject from the study.

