Alternatively, subjects may complete the Electrocardiogram (EKG) at Medical Care San Diego ([name]) and the labs (Creatinine, BUN, electrolytes and serum pregnancy test) at either the Medical Care San Diego ([name]) or a LabCorp location close to where the subject resides. Subjects who use these facilities to complete the EKG and labs will provide the PI and his staff with the test results. Subjects will need to complete these tests no more than one week prior to the first scheduled MRI scan. The research study will pay these facilities directly on the subject's behalf with the self-pay option. Once the PI receives the test results, if he feels the results are out of range he may withdraw the subject from the study.

Study Visit 1

Location: Sharp and Children's MRI Center ([name])

The morning of the imaging procedures the subject will go to the Sharp and Children's MRI Center for the scanning procedures. The medication will need to be administered 3 hours before the start of the scan.

When the subject arrives at the MRI Center, subjects will complete a urine pregnancy test. After the pregnancy test (test must be negative), the research assistant will take the subject's blood pressure and measure her heart rate and administer the study medication. The subject will complete the Taste Labeled Magnitude Scale, Hedonic Taste Preference Scale, Food Cravings Questionnaire (State), Eating Disorders Examination (EDE-Q), Temporal Experience of Pleasure Scale (TEPS), Eating Expectancy Inventory (EEI), Beck Depression Inventory (BDI-II), The Positive and Negative Affect Schedule (PANAS), and eat a standardized breakfast.

The research staff will then review study procedures and fMRI tasks.

Subjects will then complete the fMRI and structural MRI (details of tasks outlined below).

After the scan, the research assistant will take the subject's blood pressure and heart rate and will have the subject complete the Post Scan Pleasantness Ratings and the Post MRI Questionnaire.

The total length of the study visit will be approximately 4 hours (3 hours pre-scan, 1 hour scan).

Study Visit 2

Location: Sharp and Children's MRI Center ([name])

The morning of the imaging procedures the subject will go to the Sharp and Children's MRI Center for the scanning procedures. The medication will need to be administered 3 hours before the start of the scan.

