Amisulpride. Amisulpride (4-amino-N-[(1-ethylpyrrolidin-2-yl)methyl]-5-ethylsulfonyl-2-methoxy-benzamide has a bioavailability of 48% and a half-life of about 12 hours (Rosenzweig et al., 2002). It binds selectively (<https://pubchem.ncbi.nlm.nih.gov/compound/2159>) to DA D(2) and D(3) receptors in the limbic system. It reaches its peak plasma levels after 1 hour and has a second peak after 3 hours. Amisulpride does not have active metabolites (Bergemann et al., 2005). Low doses of amisulpride block presynaptic D(2)/D(3)-dopamine autoreceptors, thereby enhancing dopaminergic transmission, whereas higher doses block post-synaptic receptors, thus inhibiting DA activity (Leucht et al., 2002). In this application, we will apply a high dose to take advantage of the DA D2 receptor blocking effects of amisulpride. We are orienting our dosing on previous research using a single dose of 400mg amisulpride to block post-synaptic DA D2 receptors during fMRI (Kahnt and Tobler, 2017). That dosage showed good tolerability (Rosenzweig et al., 2002). Whether this dose is tolerable in an AN population has not been established and is a goal of this study. Establishing pharmacokinetics with plasma levels will also be important but will be part of future larger studies.

Bromocriptine. Bromocriptine is a semisynthetic, ergot alkaloid with anti-Parkinson and lactation inhibitory activities. Bromocriptine selectively binds to and activates postsynaptic DA D2-like receptors in the central nervous system (CNS), its half-life is between 2 and 8 hours, and it does not have active metabolites (<https://pubchem.ncbi.nlm.nih.gov/compound/31101>). Bromocriptine has a bioavailability of 28% and reaches its peak plasma level around 3 hours after ingestion (Holt et al., 2010). Bromocriptine has been used in fMRI previously and modulated reward and reversal learning (Cools et al., 2009). Effects of DA synthesis capacity will be tested in future larger studies. We will apply a single dose of 1.25mg bromocriptine, which was effective in manipulating both fMRI and behavior results (Cools et al., 2009; Lissek et al., 2018).

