Special Pharmacological Considerations. Bromocriptine is an anti-Parkinson medication available in the US. An investigational new drug (IND) application to the Federal Drug Administration (FDA) has been approved, IND # 141908. Amisulpride is an antipsychotic not freely available in the US; however, it can be purchased via Sanofi France as in previous studies (Admon et al., 2017). We have received an IND from the FDA, which allows for legal import of amisulpride. Both medications have a plasma peak of 3 hours, and fMRI will begin for all sessions at that time point after taking active drug or placebo. The half-lives for amisulpride of 12 hours, and 2-8 hours for bromocriptine are short enough to allow 3 days in between studies to suffice the 5 half-lives

rule for medication elimination from the body (neither medication has active metabolites) (Bergemann et al., 2005; Holt et al., 2010; Schatzberg and Nemeroff, 2013).

Handling of Study Medication

Storage Location: UC San Diego Health Eating Disorders Center for Treatment and Research, [name] (PI Office, [name])

Medications will be stored in a locked cabinet in the research office of the PI. That office is embedded in the UC San Diego Health Eating Disorders Research Program office suite, which is locked. Each study drug will be labeled with the statement “Caution: New Drug—Limited by Federal (or United States) law to investigational use.” (§312.6 Labeling of an investigational new drug.).

A randomization protocol will be developed ahead of the study using Research Randomizer (<https://www.randomizer.org>). The PI will randomize the study days for the three medications. A master file with the randomization of medication per subject will be kept by the study monitor ([name]).

While the tablets look slightly different, subjects will not be told what type of medication they receive on either day. Study participants have been drug naïve to any of the study medications, and we do not expect recognition. It is uncertain what specific effects each medication will have on brain function and there will therefore be no implicit bias.

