Each subject will complete three MRI scan days (Study Visit 1, Study Visit 2, and Study Visit 3). On each day, the subject will consume one of the three medications (amisulpride, bromocriptine or placebo). Each subject will complete a baseline scan (P-fMRI), Amisulpride scan (A-fMRI), and Bromocriptine scan (B-fMRI) spaced 3 days apart (2 to 4 day acceptable range). This randomized study has 6 medication study arms listed below:

On the morning of each study day, the PI or other study staff not running the fMRI scanning procedures will provide the study subjects the medication as per randomization. Other study personnel that will run the fMRI scanning procedures will be kept blinded from the applied medication. This will help reduce bias by the study personnel.

There are no rater applied assessments on the study days so there is no rater bias based on the personnel end. The fMRI data are objective and thus unbiased.

The investigator will not supply the investigational drug to any person not authorized under this part to receive it. (§312.61 Control of the investigational drug.)

Neither study drug is a controlled substance. Nevertheless, the study medication packages with the investigational drugs will be in a securely locked, substantially constructed cabinet, in the PI’s office, which is within an office suite that is locked and accessible only to the research personnel.

Should the subject have a serious adverse reaction that required emergency treatment, the PI would be contacted and the blinding of the medication order would be broken in order to allow adequate treatment of the patient by emergency department staff.

Each subject will be randomized to one of the following groups:

1.

Scan 1: P-fMRI
Scan 2: A-fMRI
Scan 3: B-fMRI

2.

Scan 1: P-fMRI
Scan 2: B-fMRI
Scan 3: A-fMRI

3.

Scan 1: A-fMRI
Scan 2: P-fMRI
Scan 3: B-fMRI

4.

Scan 1: A-fMRI
Scan 2: B-fMRI
Scan 3: P-fMRI

5.

Scan 1: B-fMRI
Scan 2: P-fMRI
Scan 3: A-fMRI

6.

Scan 1: B-fMRI
Scan 2: A-fMRI
Scan 3: P-fMRI

Medication dosage

Amisulpride – Single Dose 400 mg and scan 3 hours post ingestion

Bromocriptine – Single Dose 1.25 mg and scan 3 hours post ingestion

Amisulpride

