25. INVESTIGATIONAL DRUG FACT SHEET AND IND/IDE HOLDER

Drug Names: Bromocriptine mesylate; Amisulpride

IND #: 191908

IND holder: [name]

[name] and the Lab Manager will be responsible for monitoring the study in the following ways:

Medication Handling and Storage

- Per 21CFR §312.6 Labeling of an investigational new drug, medications will be stored in a locked cabinet in the research office of the PI. That office is embedded in the UCSD Eating Disorder Research Program office suite, which is locked. Each study drug will be labeled with the statement “Caution: New Drug—Limited by Federal (or United States) law to investigational use.”
- Per 21CFR §312.61 Control of the investigational drug, the investigator will not supply the investigational drug to any person not authorized under this part to receive it.

Subject Level

- [name] will review all Pre-Scan Blood Test and EKG results to ensure subject's medication risks are minimized.
- Research staff will complete symptom checklist on each Study Visit day and will document the following: Documentation of blood pressure & heart rate pre-medication administration and post scan; symptom checklist including: nausea, headache, dizziness, tiredness, other. Research Staff will report these values to [name] and the Lab Manager at the end of the Study Visit.
- Research staff will contact [name] and/or Lab Manager via phone if there is a significant drop in blood pressure (20 or more points systolic) after the medication administration or significant symptoms that the subject feels keep her from continuing the study.
- [name] or Lab Manager will confirm with research team that all unexpected or adverse events (AEs/SAEs) have been reported to the IRB and FDA in the required timeframe.
- [name] or Lab Manager will review each subject folder after the subject completes the study to ensure required documentation and procedures have been completed.

Study Level

- The Lab Manager will prepare monthly aggregate reports of the adverse events, serious adverse events, and unexpected events and will review with [name].
- [name] will review monthly aggregate reports to determine safety of the study medications and whether the study is safe to be continued.

Per FDA Approval, [name] will be responsible for the following reporting requirements:

- [name] will report any unexpected fatal or life-threatening suspected adverse reactions to FDA no later than 7 calendar days after initial receipt of the information.

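### Section 9 rules out rater bias because nothing is rater-applied on study days, but section 25 has staff complete a symptom checklist at every visit, and masking of that tolerability measure is not ensured

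*Combined protocol and SAP*

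**What the plan says.** All references are to the combined protocol and SAP.

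- **Section 9, Handling of Study Medication, on raters:** "There are no rater applied assessments on the study days so there is no rater bias based on the personnel end". The same part says that the PI or other staff not running the scans hand out the drug according to the allocation, and that the staff who run the scans are kept unaware of it. No other staff role is promised masking.
- **Section 25, Subject Level:** "Research staff will complete symptom checklist on each Study Visit day and will document the following": blood pressure and heart rate before dosing and after the scan, and a "symptom checklist including: nausea, headache, dizziness, tiredness, other".
- **Section 9, Study Visits 1 to 3, both recruitment routes:** the research assistant is to take the participant's "blood pressure and measure her heart rate and administer the study medication". After the scan the research assistant takes blood pressure and heart rate again.
- **Section 9, Amisulpride, on the dose in AN:** "Whether this dose is tolerable in an AN population has not been established and is a goal of this study". Section 7 asks whether both drugs are tolerated in AN, section 6 makes feasibility and acceptability in AN the object of Aims 1 and 2, and section 15 places side-effect assessment within the feasibility procedures.
- **Section 9, on the preparation:** Handling of Study Medication says "While the tablets look slightly different, subjects will not be told what type of medication they receive on either day". The swallow test at screening is there to "make sure she will not have any issues with the size of the medication capsules".

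**The concern.** The plan gives one reason for dismissing bias on the staff side: that nobody on the staff rates anything on study days. If staff do complete an assessment, that reason fails. The assessment in question is the one that serves the tolerability goal.

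The checklist items are soft, and the plan states which answers it expects. Section 9 anticipates nausea after amisulpride, and nausea, headache or dizziness after bromocriptine. A recorder who knows the day's drug therefore also knows which boxes to expect. Section 9 argues separately that there is no implicit bias because the drugs' effects on brain function are uncertain. That argument does not cover symptoms, whose expected pattern is written down.

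What is at stake is whether a difference in recorded symptoms between a drug day and the placebo day can be read as an effect of the drug.

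**Working it through.** No sample size, alpha or power figure enters this point, so the check sets the passages side by side.

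**Step 1. Is there a staff-completed assessment on study days?** Section 9 says no. Section 25 says yes, at each study visit. Read literally, the two cannot both hold.

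**Step 2. Is it an outcome or only a safety form?** It sits in the section on monitoring under the IND. However, sections 6, 7, 9 and 15 make acceptability, tolerability and side effects in AN something the study is to establish. The checklist is the only study-day symptom record whose content the plan specifies, so it carries that goal as well.

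**Step 3. Who may complete it, and is that person masked?**

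| Task on the study day | Who, according to the plan | Masking promised? |
|---|---|---|
| Give the drug | Research assistant (visit descriptions); PI or staff not running scans (Handling of Study Medication) | No |
| Vital signs before dosing and after the scan | Research assistant (visit descriptions); research staff (section 25) | No |
| Symptom checklist | Research staff (section 25), no role named | No |
| Run the scan | Other study personnel | Yes |

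Section 25 puts the checklist in the same record as the vital signs. The visit descriptions give those vital signs to the research assistant, who also gives the drug. A research assistant is one of the research staff. No passage separates the person who gives the drug from the person who completes the checklist, or reserves the checklist for masked staff. A site that followed the plan exactly could have the same person do both.

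**Step 4. Does the preparation settle the matter?** No. One part of section 9 speaks of tablets that look slightly different; another speaks of medication capsules. Over-encapsulation is not stated. The conclusion of Step 3 does not depend on appearance, because the drug is handed out according to the allocation by people to whom no masking is promised.

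**Step 5. How much is exposed?** Section 10 plans 44 completers, and each has 3 study visits: 44 x 3 = 132 checklists. This counts both groups, whereas the tolerability goal concerns AN. Section 10 does not split the 44. Taking the 20 per group used under Statistical Power as an assumption, the AN share would be 20 x 3 = 60 checklists, of which 20 x 2 = 40 fall on active-drug days. These are counts of exposed records, not estimates of bias.

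**The case against.** The strongest reply has four parts.

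1. **The sentence may mean something narrower.** The scan-day assessments tabulated in section 9 include no staff-scored scale, and the sentence is plausibly about such scales. This explains how it came to be written. It does not make it true as worded, and it leaves the checklist without any masking provision.
2. **Only the participant can feel these symptoms, and she is not told the drug.** This stands as a limit on the mechanism: bias would have to come through how staff ask and record. It does not remove that route.
3. **No planned estimate is affected.** The data analysis plan in section 9 specifies no drug-versus-placebo comparison of symptom rates. That is correct, and it limits the severity. Tolerability in AN is still a result the study sets out to report.
4. **The plan does not say that the checklist is unmasked.** This also stands. No passage names who completes it.

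Four stronger readings are tempting, and the documents do not support them:

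- *Every checklist is unmasked.* The text shows only that masking is not ensured.
- *The checklist decides who stops, and so which scans exist.* The stopping criteria in section 9 turn on how the participant feels and on symptoms that interfere with her functioning. None of them refers to the checklist.
- *Participants are unmasked by visibly different tablets.* The plan's term is slightly different, participants are drug naïve and recognition is not expected. Noticing that the preparations differ between days does not tell a participant which is which, and the capsule wording leaves the appearance at dosing unclear.
- *Symptom rates would be inflated by some stated amount.* The documents give no placebo symptom rate and no basis for the size of any over-recording, so any figure would be an assumption.

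**Conclusion.** The point holds in this form: the plan's only ground for excluding staff-side rater bias is contradicted by its own section 25, and masking of the tolerability measure is not ensured. This is more than a missing detail, because the plan as written allows the person who gives the drug to record the symptoms, on the premise that no such record exists.

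The direction and size of any bias cannot be computed from the documents. Up to 132 checklists are exposed across both groups. The conclusion assumes that the checklist is used to judge tolerability, as sections 7, 9 and 15 indicate, and that a person handing out the drug according to the allocation may know what it is.

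The fMRI outcomes are not directly affected, since the staff who run the scans are to be kept unaware of the drug. The change should be made, but the point does not threaten the imaging hypotheses.

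**What to change.** 1. In section 9, Handling of Study Medication, delete the sentence on rater-applied assessments, or correct it to acknowledge the checklist and vital signs in section 25.
2. In section 25, name who completes the checklist. Either the participant fills it in herself, or staff kept unaware of the day's drug do so. Have the post-scan vital signs recorded by masked staff as well.
3. State that whoever hands over the drug takes no part in symptom rating.
4. Reconcile the visit descriptions with Handling of Study Medication on who gives the drug: the research assistant, or the PI and staff not running scans. The two agree only if that research assistant never runs the scans, and the plan should say so if that is meant.
5. Reconcile the swallow-test wording (capsules) with Handling of Study Medication (tablets that differ slightly), and state what the participant and the person giving the drug actually see.

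The cost is a small reassignment of tasks on the study day, or one short extra form for a participant who already completes several questionnaires at each visit. Section 9 already separates those who hand out the drug from those who run the scans. The plan does not show that the scanning staff are free to take on the post-scan recording, so the site should confirm this before choosing that option.
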